### 3.8.3. Selection of Non-Efficacy Data in the Event of Multiple Records in an Analysis Visit Window

Depending on the statistical analysis method, single values may be required for each analysis window. For example, change from baseline by visit usually requires a single value, whereas a time-to-event analysis would not require 1 value per analysis window.

If multiple valid, nonmissing, continuous measurements exist in an analysis window, records will be chosen based on the following rules if a single value is needed:

- In general, the baseline value will be the last nonmissing value on or prior to the first dosing date of study drug, unless specified differently. If multiple measurements occur on the same day, the last nonmissing value prior to the time of first dosing of study drug will be considered as the baseline value. If these multiple measurements occur at the same time or the time is not available, the average of these measurements (for continuous data) will be considered the baseline value.
- For postbaseline visits:
  - The record closest to the nominal day for that visit will be selected.
  - If there are 2 records that are equidistant from the nominal day, the later record will be selected.
  - If there is more than 1 record on the selected day, the average will be taken, unless otherwise specified.

If multiple valid, nonmissing, categorical measurements exist in an analysis window, records will be chosen based on the following rules if a single value is needed:

- For baseline, the last available record on or prior to the date of the first dose of study drug will be selected. If there are multiple records with the same time or no time recorded on the same day, the value with the lowest severity will be selected (eg, normal will be selected over abnormal for safety ECG findings).
- For postbaseline visits:
  - The record closest to the nominal day for that visit will be selected.
  - If there are 2 records that are equidistant from the nominal day, the later record will be selected.
  - If there is more than 1 record on the selected day, the value with the worst severity will be selected (eg, abnormal will be selected over normal for safety ECG findings), unless otherwise specified.

The rules for selecting efficacy data in the event of multiple records in an analysis visit window are specified in Section [6.1](#).

## 4. SUBJECT DISPOSITION

### 4.1. Subject Enrollment and Disposition

A summary of subject enrollment will be provided by treatment group for each country within each geographic region and investigator within a country. The summary will present the number and percentage of subjects enrolled. For each column, the denominator for the percentage calculation will be the total number of subjects analyzed for that column.

A similar enrollment table will be provided by stratification factor stratum. The denominator for the percentage of subjects in the stratum will be the total number of enrolled subjects. If there are discrepancies in the value used for stratification assignment between the IWRS and the clinical database, the value collected in the clinical database will be used for the summary. A listing of subjects with discrepancies in the value used for stratification assignment between the IWRS and the clinical database at the time of data finalization will be provided.

The randomization schedule used for the study will be provided in a listing as an appendix to the CSR.

A summary of subject disposition will be provided by treatment group. This summary will present the number of subjects screened, the number of subjects not randomized, the number of subjects who met all eligibility criteria but were not randomized with reasons subjects were not randomized, the number of subjects randomized, and the number of subjects in each of the categories listed below:

- Safety Analysis Set
- Full Analysis Set
- Per-Protocol Analysis Set
- PK Analysis Set
- **CCI**
- Continuing study drug (Week 24 Analysis only)
- Completed study drug
- Did not complete study drug with reasons for premature discontinuation of study drug
- Continuing study (Week 24 Analysis only)
- Completed study
- Did not complete study with reasons for premature discontinuation from the study

For the status of study drug and study completion, and reasons for premature discontinuation, the number and percentage of subjects in each category will be provided. The denominator for the percentage calculation will be the total number of subjects in the Safety Analysis Set corresponding to that column.

The following by-subject listings will be provided by subject ID number in ascending order to support the above summary tables:

- Reasons for premature study drug or study discontinuation
- Reasons for screen failure (will be provided by screening ID number in ascending order)
- Lot number and kit ID of assigned study drugs

#### **4.2. Extent of Study Drug Exposure and Adherence**

Extent of exposure to study drug will be examined by assessing the total duration of exposure to study drug and the level of adherence to the study drug specified in the protocol.

##### **4.2.1. Duration of Exposure to Study Drug**

Total duration of exposure to any study drug will be defined as last dosing date of any study drug minus first dosing date of any study drug plus 1, regardless of any temporary interruptions in study drug administration, and will be expressed in weeks using up to 1 decimal place (eg, 4.5 weeks).

Total duration of exposure to individual study drug will be defined as last dosing date of individual study drug minus first dosing date of individual study drug plus 1, regardless of any temporary interruptions in study drug administration, and will be expressed in weeks using up to 1 decimal place.

For subjects with a partial last dosing date (ie, month and year of last dose are known), the latest of the dispensing dates of study drug bottles, study drug start dates and end dates, and the imputed last dosing date (day imputed as 15) will be used as the final imputed last dosing date. If the subject died and the death date is complete (ie, not partial date) and before the imputed last dosing date, the complete death date will be used as the imputed last dosing date.

If only year is recorded (ie, month and day of last dose are missing), the latest of the dispensing month of study drug bottles, study drug start month, and study drug end month will be used to impute the unknown last dose month. If the subject died and the death date has month and year available and before the imputed last dose month, then the month of death will be used instead. With the month imputed, the aforementioned method will be used to impute the last dose date.

If subjects are continuing on study drug at Week 24 analysis, the earliest of the date of death or data cutoff date for Week 24 analysis will be used to impute the last dosing date for the calculation of duration of exposure to study drug.

The total duration of exposure to any study drug and total duration of exposure to each individual study drug will be summarized using descriptive statistics and using the number (ie, cumulative counts) and percentage of subjects exposed through the following time periods: Baseline (Day 1), Week 2 (Day 15), Week 4 (Day 29), Week 8 (Day 57), Week 12 (Day 85), Week 16 (Day 113), Week 20 (Day 141), Week 24 (Day 169), Week 30 (Day 211), Week 36 (Day 253), Week 44 (Day 309), and Week 52 (Day 365).

Summaries will be provided by treatment group for the Safety Analysis Set. No formal statistical testing is planned.

#### **4.2.2. Adherence to Study Drug**

Adherence will be calculated separately for filgotinib 200 mg/PTM (tablets), filgotinib 100 mg/PTM (tablets).

The total number of tablets administered will be summarized using descriptive statistics.

The presumed total number of tablets administered to a subject will be determined by the data collected on the drug accountability CRF using the following formula:

Total Number of Tablets or Capsules Administered

$$= \left( \sum \text{No. of Tablets Dispensed} \right) - \left( \sum \text{No. of Tablets Returned} \right)$$

If a bottle is dispensed and the bottle is returned empty, then the number of tablets returned will be entered as zero. If a bottle is dispensed but not returned (missing), the number of tablets administered will be counted as zero by assuming that a subject did not take study drug as prescribed during the period for which the bottle was dispensed.

##### **4.2.2.1. On-Treatment Adherence**

The level of on-treatment adherence to the study drug will be determined by the total amount of study drug administered relative to the total amount of study drug expected to be administered during a subject's actual on-treatment period based on the study drug regimen.

The level of on-treatment adherence will be expressed as a percentage using the following formula:

$$\text{On-Treatment Adherence (\%)} = \left( \frac{\text{Total Amount of Study Drug Administered}}{\text{Study Drug Expected to be Administered on Treatment}} \right) \times 100$$

Note: If calculated adherence is greater than 100%, the result will be set to 100%.

Study drug expected to be administered for filgotinib 200 mg/PTM (tablets) =  $1 \times$  total duration of exposure to any study drug (days).

Study drug expected to be administered for filgotinib 100 mg/PTM (tablets) =  $1 \times$  total duration of exposure to any study drug (days).

On-treatment adherence will be calculated up to Week 24 and up to Week 52.

Descriptive statistics for the level of on-treatment adherence with the number and percentage of subjects belonging to adherence categories (eg,  $< 80\%$ ,  $\geq 80\%$  to  $< 90\%$ ,  $\geq 90\%$ ) will be provided by treatment group for the Safety Analysis Set.

Categorical displays will be presented for the number of subjects who are at least 80% adherent to their study drug regimen (ie, adherence is  $\geq 80\%$  for each study drug).

No formal statistical testing is planned.

A by-subject listing of study drug administration and drug accountability will be provided separately by subject ID number (in ascending order) and visit (in chronological order).

### **4.3. Protocol Deviations**

Subjects who did not meet the eligibility criteria for study entry, but enrolled in the study will be summarized regardless of whether they were exempted by the sponsor or not. The summary will present the number and percentage of subjects who did not meet at least 1 eligibility criterion and the number of subjects who did not meet specific criteria by treatment group based on the All Randomized Analysis Set. A by-subject listing will be provided for those subjects who did not meet at least 1 eligibility (inclusion or exclusion) criterion. The listing will present the eligibility criterion (or criteria if more than 1 deviation) that subjects did not meet and related comments, if collected.

Protocol deviations occurring after subjects entered the study are documented during routine monitoring. The number and percentage of subjects with important protocol deviations by deviation reason (eg, nonadherence to study drug, violation of select inclusion/exclusion criteria) will be summarized by treatment group for the All Randomized Analysis Set. A by-subject listing will be provided for those subjects with important protocol deviation.

## 5. BASELINE CHARACTERISTICS

### 5.1. Demographics and Other Baseline Characteristics

Subject demographic variables will be summarized by treatment group and overall using descriptive statistics for continuous variables, and using number and percentage of subjects for categorical variables. The summary of demographic data will be provided for the Safety Analysis Set for the following:

- Age (on the first dose date of any study drug)
- Age group (< 65 years, ≥ 65 years)
- Sex at birth (male, female)
- Race
- Ethnicity (Hispanic or Latino, not Hispanic or Latino)
- Geographic region and country
- Weight
- Height
- Body mass index (BMI; in kg/m^2)
- Smoking status

A by-subject demographic listing, including the informed consent date, will be provided by subject ID number in ascending order.

### 5.2. Baseline Disease Characteristics

Baseline disease characteristics include:

- Duration of RA from diagnosis (years)

Calculated as ((first dose date) – (date of initial diagnosis) + 1 day) / 365.25. If the date of initial diagnosis is incomplete, then the following rules will be applied:

— missing day: use the first of the month.

— missing month: use January.

- Presence of RF (Yes/No)
- Presence of anti-CCP Ab (Yes/No)

- Presence of RF and anti-CCP Ab (Yes/No)
- Concurrent oral corticosteroid use on the first dosing date (Yes/No): n(%)
  - Oral corticosteroids dose, mg/day, expressed as prednisone-equivalent dose, mean (SD)
- Concurrent anti-malarials use on the first dosing date (Yes/No): n(%)
- DMARD and investigational bDMARD naïve
- Swollen joint count based on 66 joints (SJC66)
- Tender joint count based on 68 joints (TJC68)
- Swollen joint count based on 28 joints (SJC28)
- Tender joint count based on 28 joints (TJC28)
- HAQ-DI total score
- DAS28(CRP)
- SF-36 PCS score
- SF-36 MCS score
- FACIT-Fatigue
- Subject's global assessment of disease activity (SGA, by visual analog scale [VAS] in mm)
- Physician's global assessment (PGA, by VAS in mm)
- Subject's pain assessment (by VAS in mm)
- Simplified Disease Activity Index (SDAI)
- Clinical Disease Activity Index (CDAI)
- hsCRP (mg/L)
- mTSS
  - Erosion score
  - Joint space narrowing score

These baseline characteristics will be summarized by treatment group and overall using descriptive statistics for continuous variables and using number and percentage of subjects for categorical variables. The summary of baseline characteristics will be provided for the Safety Analysis Set.

A by-subject listing of other baseline characteristics will be provided by subject ID number in ascending order.

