### 3.4. Examination of Subject Subgroups

The primary and key secondary efficacy endpoints will be examined using the following subgroups (but not limited to the ones listed below):

- Age (on the first dosing date of any study drug, < 65 or ≥ 65)
- Sex at birth (male, female)
- Race
- Baseline weight ( < 60 kg, ≥ 60 to < 100 kg, ≥ 100 kg)
- Geographic region (A, B, C, or E)
- Presence of RF or anti-CCP Ab (Yes or No)
- Duration of RA diagnosis on the first dosing date of any study drug (< 1 year, ≥ 1 to < 2 years, ≥ 2 years)
- Disease activity at Baseline (DAS28[CRP] ≤ 5.1 or DAS28[CRP] > 5.1)
- Concurrent use of oral systemic corticosteroids on the first dosing date of any study drug (Yes or No)
- High-sensitivity C-reactive protein (hsCRP) at baseline (≥ 4 mg/L, < 4 mg/L)

Lists of oral systemic corticosteroids are provided in [Appendix 1](#).

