### **3.6. Missing Data and Outliers**

#### **3.6.1. Missing Data**

In general, missing data will not be imputed unless methods for handling missing data are specified. Exceptions are presented in this document.

For missing last dosing date of study drug, imputation rules are described in Section 4.2.1. For partial date of initial RA diagnosis, imputation rules are described in Section 5.2. The handling of missing or incomplete dates for AE onset is described in Section 7.1.5.2, and for prior and concomitant medications in Section 7.4. Imputation rules adopted in the efficacy analyses are specified in Section 6.

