### **3.7. Data Handling Conventions and Transformations**

In general, age (in years) on the date of the first dose of study drug will be used for analyses and presentation in listings. If an enrolled subject was not dosed with any study drug, the randomization date will be used instead of the first dosing date of study drug. For screen failures, the date the last informed consent was signed will be used for age calculation. If only birth year is collected on the CRF, “01 July” will be used for the unknown birth day and month for the purpose of age calculation. If only birth year and month are collected, “01” will be used for the unknown birth day.

Non-PK Data that are continuous in nature but are less than the lower limit of quantitation (LOQ) or above the upper LOQ will be imputed as follows:

- A value that is 1 unit less than the LOQ will be used to calculate descriptive statistics if the datum is reported in the form of “< x” (where x is considered the LOQ). For example, if the values are reported as < 50 and < 5.0, values of 49 and 4.9, respectively, will be used to calculate summary statistics. An exception to this rule is any value reported as < 1 or < 0.1, etc. For values reported as < 1 or < 0.1, a value of 0.9 or 0.09, respectively, will be used for calculate summary statistics.
- A value that is 1 unit above the LOQ will be used to calculate descriptive statistics if the datum is reported in the form of “> x” (where x is considered the LOQ). Values with decimal points will follow the same logic as above.
- The LOQ will be used to calculate descriptive statistics if the datum is reported in the form of “≤ x” or “≥ x” (where x is considered the LOQ).

Natural logarithm transformation will be used for plasma/blood concentrations and analysis of PK parameters. Plasma concentration values that are below the limit of quantitation (BLQ) will be presented as “BLQ” in the concentration data listing. Values that are BLQ will be treated as 0 at predose time points, and one-half the value of the LOQ at postbaseline time points.

The following conventions will be used for the presentation of summary and order statistics:

- If at least 1 subject has a concentration value of BLQ for the time point, the minimum value will be displayed as “BLQ.”
- If more than 25% of the subjects have a concentration data value of BLQ for a given time point, the minimum and Q1 values will be displayed as “BLQ.”

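### Year-only RA diagnosis dates are set to 1 January, which pushes subjects near the 1- and 2-year cuts into the longer-duration subgroups; a mid-year rule would be a cheap improvement

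*SAP*

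**What the plan says.** SAP 5.2 defines RA duration as follows: "Calculated as ((first dose date) – (date of initial diagnosis) + 1 day) / 365.25". For an incomplete diagnosis date it gives two rules: "missing day: use the first of the month" and "missing month: use January". Applied together, they turn a year-only date into 1 January of that year.

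No other rule applies. SAP 3.6.1 refers back to the same place: "For partial date of initial RA diagnosis, imputation rules are described in Section 5.2". No sensitivity analysis on this variable is planned.

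SAP 3.4 lists "Duration of RA diagnosis on the first dosing date of any study drug" as a subgroup factor with three levels: under 1 year, 1 to under 2 years, and 2 years or more. Of the whole list it says "The primary and key secondary efficacy endpoints will be examined using the following subgroups". SAP 6.2.5 and 6.3.4 then compare each filgotinib group with MTX alone within each level.

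For birth dates the SAP takes a different line. When only the year is known, SAP 3.7 states that 01 July "will be used for the unknown birth day and month". When only the day is unknown, SAP 3.7 uses the first of the month, as SAP 5.2 does.

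**The concern.** Setting an unknown date to its earliest possible value can only lengthen the derived duration. That matters little when the variable is coarse compared with the error. Here the error can approach a full year and the cuts are at 1 and 2 years.

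Take a subject diagnosed on 15 November and first dosed on the following 15 February. The true duration is 93/365.25 = 0.25 years. With only the year recorded, SAP 5.2 gives 411/365.25 = 1.13 years, and the subject leaves the under-1-year group.

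At stake are the content of the early-disease subgroup and the reported baseline duration. Subjects whose disease really is recent would be displayed with those of longer duration, and no error in the other direction would offset this.

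**Working it through.** The plan gives no figure on this point, so there is none to reproduce. The formula, the imputation rules and the cuts come from SAP 5.2 and 3.4. The distribution of dates within the year and the number of year-only dates are not in the documents. Write Y for the calendar year of first dose.

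**1. Shortest imputed duration.** This arises with a first dose on 1 January.
- Year-only diagnosis in Y−1: (365 + 1)/365.25 = 1.0021 years, or 367/365.25 = 1.0048 if Y−1 is a leap year.
- Year-only diagnosis in Y−2: (730 + 1)/365.25 = 2.0014 years, or 732/365.25 = 2.0041 with a leap year between.

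Every dosing day in four assumed years (2016 to 2019) was checked. None gives under 1 year for a Y−1 diagnosis, and none gives under 2 years for a Y−2 diagnosis. This step needs no distributional assumption.

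**2. Share that truly belongs below the cut.** Let u be the dosing date and v the diagnosis date, each as a fraction of its year. Assume both are uniform and independent. For a Y−1 diagnosis:
- true duration = 1 + u − v, which is below 1 when v > u, so the probability is 0.5;
- imputed duration = 1 + u, which is never below 1, so about 50% are misclassified, all upward.

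Counting calendar days instead gives 49.7% to 49.9% at the 1-year cut and 49.6% to 49.9% at the 2-year cut.

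**3. Sensitivity of that share** (Y−1 diagnoses, 1-year cut, Y = 2017):

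| Assumption | Truly under 1 year |
|---|---|
| Dosed in January | 95% |
| Dosed in June | 54% |
| Dosed in December | 4% |
| Durations exponential, mean 10 years | 51% |
| Mean 2 years | 58% |
| Mean 1 year | 66% |
| Mean 0.5 year | 79% |

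**4. Overstated duration.** For a year-only diagnosis in an earlier calendar year, imputed minus true duration is v, with mean 0.5 years under uniform dates. For a diagnosis in the dosing year the error is smaller, because v cannot exceed u. Those subjects stay under 1 year, except for dosing on 31 December of a leap year (1.0021).

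**5. The 01 July alternative.** The imputed duration for a Y−1 diagnosis is 0.5 + u, below 1 when u < 0.5.
- Dosed in the first half-year: wrong with probability u, mean 0.25.
- Dosed in the second half-year: wrong with probability 1 − u, mean 0.25.

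Overall 25% are wrong, in both directions. The mean error in duration is E[v] − 0.5 = 0. By calendar count (2017 and 2018), 49.6% are classed under 1 year against a true 49.7% to 49.9%, with 25.0% to 25.1% misclassified.

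**6. Missing day only.** The mean overstatement is about half a month (0.5/12 = 0.04 years). About 4% of month-known Y−1 diagnoses change category.

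**The case against.** The strongest reply is that this is a fixed, pre-specified convention, identical in every arm and applied to a baseline variable. Comparisons within a subgroup as defined therefore remain randomised. RA duration is one of ten listed subgroup factors. It is not a stratification factor (SAP 3.3), not a named model covariate (SAP 6.2.3 and 6.3.2) and not in the testing order (SAP 3.5). All of that stands. A reader might infer from the mention of primary and key secondary endpoints that their tests are at risk. The documents do not support that, since only the subgroup displays use this variable.

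A second reply concerns size. One could assume a share of year-only dates and derive a percentage of the trial in the wrong subgroup, but the documents give no such share. Recent diagnoses may also be the best dated: Protocol 6.2.1 collects RA onset at Screening, and Protocol 9.1.5 requires source documentation confirming the diagnosis. If year-only dates cluster in long-standing disease, the effect at the cuts approaches zero. This also stands.

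A third reply is that the midpoint only trades one error for another, since January never puts a subject with a true duration of 1 year or more into the under-1-year group. This does not hold up. Under uniform diagnosis dates, 01 July gives the same category as January for second-half dosing and the more likely category for first-half dosing.

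It is also tempting to extend the criticism to missing days. That is not supported: the effect is negligible, and SAP 3.7 itself uses the first of the month for an unknown birth day.

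**Conclusion.** The point holds for year-only dates. It is exact that a year-only diagnosis in the calendar year before dosing is always classed as 1 year or more, and one from two calendar years before as 2 years or more. That about half of these are misclassified is conditional on uniform, independent dates. It is an average over dosing months, not a property of any one subject, and it rises if recent diagnoses predominate. The overstatement of about 0.5 years is a mean over year-only subjects under the same assumption. Each 1% of subjects with such a date would move the trial mean by only 0.5 × 0.01 = 0.005 years.

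The trial-level effect cannot be sized from the documents. It is confined to the baseline duration summary and the RA-duration subgroup displays. This is a cheap improvement, not a threat to the trial's conclusions.

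**What to change.** In SAP 5.2, impute a missing day and month of diagnosis as 01 July, as SAP 3.7 does for birth dates. If that date falls after informed consent, use the midpoint between 01 January of that year and the consent date. Leave the rule for a missing day alone (first of the month) unchanged.

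The cost is a sentence or two in the SAP and one fallback rule to program. About 25% of year-only dates in the two calendar years before the dosing year would still be misclassified under uniform dates, but no longer all in one direction.
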